9. How often did pain keep you from socializing with others?					

ROCKS PRO LURN-S10

Instruction: This questionnaire asks you about different urinary symptoms. Please read each question carefully, and then circle the response that best describes your symptoms.

	Never	A few times	About half the time	Most of the time	Every time
1. In the past 7 days, how often did you feel a sudden need to urinate?	0	1	2	3	4
2. In the past 7 days, how often did you leak urine or wet a pad after feeling a sudden need to urinate?	0	1	2	3	4
3. In the past 7 days, how often did you leak urine or wet a pad while laughing, sneezing, or coughing?	0	1	2	3	4
4. In the past 7 days, how often did you leak urine or wet a pad when doing physical activities, such as exercising or lifting a heavy object?	0	1	2	3	4
5. In the past 7 days, how often did you have pain or discomfort in your bladder while it was filling?	0	1	2	3	4
6. In the past 7 days, how often did you have a delay before you started to urinate?	0	1	2	3	4
7. In the past 7 days, how often was your urine flow slow or weak?	0	1	2	3	4
8. In the past 7 days, how often did you dribble urine just after zipping your pants or pulling up your underwear?	0	1	2	3	4
	Circle number here -->	0	1	2	3
9. In the past 7 days, during waking hours, how many times did you typically urinate?	(3 or fewer times a day)	(4-7 times a day)	(8-10 times a day)	(11 or more times a day)	
	Circle number here -->	0	1	2	3
10. In the past 7 days, during a typical night, how many times did you wake up and urinate?	(none)	(1 time)	(2-3 times)	(More than 3 times)	

ROCKS PRO ICIQ-S

Answer the following questions thinking about how satisfied you were with the treatment or surgery that you had. All the information you give us is confidential.

1. How would you rate the outcome of your surgery?

very successful		4
somewhat successful		3
neither successful nor unsuccessful		2
a little unsuccessful		1
very unsuccessful		0

2. Compared to how you felt before your surgery, how is your condition now?

much better		4
a bit better		3
about the same		2
a bit worse		1
much worse		0

3. Would you say you have been able to return to a 'normal life' after your surgery?

strongly agree (or I was not limited before)		3
agree		2
disagree		1
strongly disagree		0

4. If you were in the same situation again, would you still have the surgery?

yes, definitely		4
yes, probably		3
not sure		2
no, probably not		1
no, definitely not		0

5. Would you recommend this surgery to friends or relatives with similar problems?

yes, definitely		4
yes, probably		3
not sure		2
no, probably not		1
no, definitely not		0

6. If you had to spend the rest of your life with your symptoms as they are now, how would you feel?

perfectly happy (or I no longer have any symptoms)		5
somewhat happy		4
mixed feelings		3
somewhat unhappy		2
very unhappy		1
desperate		0

ROCKS PRO Time Off Work

Within the last week, did you miss any days of school or work?

- Yes
 - No
 - I do not currently work/I am not currently in school

If yes, please enter how many days of school or work were missed.

Within the last week, has your parent/caregiver missed work?

- Yes
 - No
 - My parent/caregiver does not currently work

If yes, please enter how many days of work your parent/caregiver has missed.

[figure not shown]
[figure not shown]
ROCKS PRO USSQ

USSQ question concerning stent

Instruction: Answer the question below if you had a stent placed during the surgical procedure otherwise select N/A.

Figure 2. Daily Ecological Momentary Assessment

Visual Analog Pain Scale

PROMIS® Ability to Participate in Social Roles and Activities – Short Form 4a Questionnaire

	Never	Rarely	Sometimes	Usually	Always
SRPPER23_CaPS	 5	 4	 3	 2	 1

[figure not shown]
[figure not shown]
Figure 3. BLUES Patient Reported Outcomes: Flow Chart

Figure 4. BLUES Ecological Momentary Assessments (EMA) – Daily Text Survey: Flow Chart

APPENDICES

Appendix 1. Heat map of appropriateness for ureteral stent omission after URS according to panelists

		Pre Stented						
		Negative Culture						
		Size ≤5mm		Size >5mm - ≤10mm		Size >10mm - ≤15mm		
No Dilation	Ureter	Ureter	Kidney	Ureter	Kidney	Ureter	Kidney	
	UAS -	Frag -	9	9	9	9	7	7
	UAS +	Frag -	8	8	8	7	6	6
	UAS -	Frag +	7	7	7	6	5	4
	UAS +	Frag +	7	7	6	5	3	4
		Not Pre Stented						
		Negative Culture						
		Size ≤5mm		Size >5mm - ≤10mm		Size >10mm - ≤15mm		
No Dilation	Ureter	Ureter	Kidney	Ureter	Kidney	Ureter	Kidney	
	UAS -	Frag -	9	9	7	7	5	4
	UAS +	Frag -	3	3	3	2	2	2
	UAS -	Frag +	6	5	3	2	2	1
	UAS +	Frag +	3	2	2	2	1	1
Dilation		Highly Appropriate	Appropriate	Uncertain	Inappropriate	Highly Inappropriate		
		Median = 9	Median = 7-8	Median = 4-6	Median = 2-3	Median = 1		

UAS +, ureteral access sheath used. UAS -, no ureteral access sheath used. Frag +, basketable residual fragments left. Frag -, no basketable residual fragments left

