Immediate. Based upon prior RCT outside of the United States, the use of silicone ureteral stents has the potential to decrease pain and LUTS after URS.(12) Decreased pain and LUTS after URS secondarily could decrease the rate of ambulatory healthcare utilization, opioid prescriptions, postoperative ED visits, and unplanned hospitalizations. It could also decrease the number of days required to miss work due to recovery.

Long-range. Decreased pain and LUTS after URS secondarily could decrease a patient's exposure to opioid analgesia postoperatively. Less patient requirements for opioid analgesia could decrease the incidence of new persistent long-term use of opiates in these patients.

Section 5: STUDY OBJECTIVES**Section 5.1: Primary Objectives**

1. To determine the health-related quality of life and symptoms in patients with urinary stone disease stented with silicone or polyurethane stents at ureteroscopy.

Section 5.2: Secondary Objectives

1. To compare 30-day emergency department visits and hospitalization rates between study arms
2. To compare rates and intensity of ambulatory healthcare encounters after ureteroscopy and stenting between study arms
3. To compare stone-free rates between study arms
4. To compare abnormal imaging findings after ureteroscopy and stenting between study arms

Section 5.3: Exploratory Objectives

1. To compare days taken off work by patient between study arms
2. To compare days taken off work by caregiver between study arms
3. To compare Ecological Momentary Assessments (EMA) measured via daily text message for 10 days between study arms
4. To compare Composite score difference between Winratio and Desirability Of Outcome Ranking (DOOR) between study arms
5. To compare number of patients receiving opioid prescriptions between study arms
6. To compare ICIQ-s score at 7 days between study arms
7. To compare ICIQ-s score at 4 weeks between study arms

Section 5.4: Endpoints

- Primary Efficacy Endpoint(s):
 - Silicone stent placement will be associated with significantly improved PROMIS® scores of pain intensity and interference at 7 days compared to non-silicone stent placement.
- Secondary Efficacy Endpoint(s):
 - Silicone stent placement will be associated with equivalent PROMIS® scores of pain intensity and interference at 4 weeks compared to non-silicone stent placement.

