Participating BLUES practices will utilize the MUSIC Registry and ROCKS PRO as a tool to enroll and collect patient surveys. Through ROCKS PRO, patients are provided via email a secure and unique link to the MUSIC Registry patient portal. An electronic introduction for ROCKS PRO will then be presented. Patients will not be required to participate and may choose to be removed from future correspondence by emailing or calling the MUSIC Coordinating Center directly.

If participating, they will be directed to the baseline questionnaire consisting of questions regarding health-related symptoms, functions and pain management before undergoing ureteroscopy. Automated email survey links will be sent to patients to complete ROCKS PRO questionnaires pre-operatively and at 7 days, and 4 weeks after surgery (Figure 1). Patients with cell phone numbers who agree to participate in BLUES will be asked to complete EMA of pain via a visual analog scale score and one question from the PROMIS® Ability to Participate in Social Roles and Activities Questionnaire (Figure 2), for 10 days after surgery.

If a patient does not log-in or fails to complete the baseline survey, they will receive an electronic automated reminder and will be contacted by the MUSIC Coordinating Center. If a patient does not log-in or fails to complete the 7-day survey, they will receive an electronic automated reminder and will be contacted by the MUSIC Coordinating Center on day 8 and 9, to facilitate its completion by the end of post-operative day 10. The BLUES Study Team may also administer the PRO questionnaires via REDCap, phone, or paper if the participant is unable to complete surveys through the MUSIC Registry.

Figure 3 depicts the timeline and flow chart of the recruitment and follow-up process. If it is past the patient's operative date they will not be enrolled or contacted.

The patient's surgery will proceed per standard of care, and their follow up, imaging and clinic visits will be directed by the local surgeon according to their local protocol. The BLUES study is pragmatic. Stents will be removed at a time and duration per the surgeon's discretion. The patient's information regarding post-operative course will be collected into the registry 60 days after the surgery, keeping with current practice for MUSIC ROCKS patient registry entry.

Section 8.2: Operative

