An interim analysis for futility is planned after accrual of 112 patients. The study will stop early if it is found that the silicone stent arm has clinically significant worse pain intensity and worse pain interference at 7 days with worse pain defined as 5 or greater t-score points worse pain in the silicone stent arm compared to the non-silicone stent arm after adjusting for baseline. Under the alternative hypothesis for both endpoints simulations of 1000 trials estimates the probability of stopping early is 0%. If we assume that the silicone stent is worse than the non-silicone stent by 5 points simulation of 1000 trials estimates the probability of stopping early is 24.4%.

Section 11: STATISTICAL CONSIDERATIONS

Section 11.1: Statistical Hypotheses

This is a multi-center two-arm stratified, randomized comparative effectiveness study in patients are treated with URS for nephrolithiasis with a planned placement of a stent to assess patient reported quality of life. The primary hypothesis is that the silicone ureteral stent arm will have superior patient reported pain outcomes compared to the non-silicone stent arm. Patients will be stratified by stone location (kidney only / ureteral) and randomized to receive a silicone stent or a non-silicone stent and complete the PROMIS® pain intensity and PROMIS® pain interference surveys prior to surgery and at 7 days after stent placement.

Our formal statistical hypotheses are:

$$H_0: \mu_{ns} = \mu_{ss}, \quad H_1: \mu_{ns} \neq \mu_{ss}$$

where, μ_{ns} = mean PROMIS® pain intensity in non-silicone stent arm at 7 days

μ_{ss} = mean PROMIS® pain intensity in silicone stent arm at 7 days

AND

$$H_0: w_{ns} = w_{ss} \quad H_1: w_{ns} \neq w_{ss}$$

where, w_{ns} = mean PROMIS® pain interference in non-silicone stent arm at 7 days

w_{ss} = mean PROMIS® pain interference in silicone stent arm at 7 days

Section 11.2: Power/Sample Size:

Assume that the correlation of baseline is 0 for purposes of the sample size calculation. If this assumption is violated, the power for each hypothesis will be greater than the stated power.

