In addition to the WinRatio, our second composite analysis will include healthcare utilization and PROMIS® Pain. Additionally, we will use a composite score ranking of healthcare utilization similar to the WinRatio plan and add the PROMIS® Pain scores to the analysis using DOOR. The probability that a randomly selected patient will have a better DOOR if assigned to the silicone stent will be estimated.(21) The WinRatio and DOOR composite healthcare utilization metric ratios' sizes and directions will be compared.

The number and proportion of patients who are prescribed opioid medications will be reported by arm and compared using a chi-square test.

Satisfaction score assessed using the ICIQ-S will be summarized at 7 days and 4 weeks by arm with means and standard deviations. A repeated measures model will be used to test if satisfaction differed at either time between treatment arms using an interaction of time and arm.

Section 12: DATA AND SAFETY MONITORING

The DSMC will consist of the MUSIC ROCKS Program Manager, Program Director, Statistician, and other members of the MUSIC ROCKS team. This committee is responsible for monitoring the safety and data integrity of the study.

Each performance site's local study team is required to meet virtually with the DSMC and BLUES study team every six months if it is determined by the DSMC and/or Principal Investigator that a virtual meeting is necessary. The discussion may include matters related to the safety of study participants (Serious Adverse Event, Adverse Event and Unanticipated Problem reporting), completeness, validity and integrity of the study data, enrollment rate relative to expectations, characteristics of participants, retention of study participants, and adherence to the protocol (potential or real protocol deviations). If there are no concerns around any of the aforementioned items, the principal investigator and/or the DSMC may decide that a meeting is unnecessary and if so, a progress summary communication will serve in its place. Additionally, a member of the BLUES study team will send a communication summarizing current progress to each site on a monthly basis. These communications will consist of 1) any identified Serious Adverse Events and necessary follow-up, 2) enrollment rate relative to expectations, and 3) any identified protocol deviations, unanticipated problems, and recommendations to prevent additional instances.

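### The exploratory ICIQ-S model omits pre-operative covariates already collected, and its interaction test does not give the arm difference at each visit; possible loss of precision, no bias

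*Combined protocol and SAP*

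**What the plan says.** **Instrument (Figure 1, ICIQ-S).** Item 2 asks "Compared to how you felt before your surgery, how is your condition now", scored 0 to 4. The top category of item 3, worth 3 points, begins "strongly agree (or I was not limited before". The other four items have no such reference. Item 1 asks "How would you rate the outcome of your surgery", items 4 and 5 ask about having the surgery again and recommending it, and item 6 asks "If you had to spend the rest of your life with your symptoms as they are now, how would you feel".

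**Status and hypotheses.** ICIQ-S is exploratory. Section 5.3 lists "To compare ICIQ-s score at 7 days between study arms" and a matching objective at 4 weeks. Section 5.4 expects better scores in the silicone arm at each of the two visits.

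**Analysis (Section 11.4, Exploratory Analyses).** Means and standard deviations are reported by arm at both visits. Then: "A repeated measures model will be used to test if satisfaction differed at either time between treatment arms using an interaction of time and arm". No baseline covariate is named, and no general rule elsewhere in Section 11 adds one.

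**Pre-operative data.** Section 8.1 says "Automated email survey links will be sent to patients to complete ROCKS PRO questionnaires pre-operatively and at 7 days, and 4 weeks after surgery". Section 11.1 has patients complete the "pain interference surveys prior to surgery and at 7 days after stent placement". Section 5.4 defines LURN SI-10 endpoints relative to baseline, so that score is needed before surgery too. Section 7 ties the surgeon's notification of the allocation to a completed baseline questionnaire.

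**Contrast.** The primary PROMIS models in Section 11.4 adjust for baseline. Section 11.2 explains that this handles imbalance before surgery and raises power when the correlation exceeds 0.

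**The concern.** Part of the ICIQ-S score can reflect how the patient was before surgery rather than which stent was placed. A patient with few symptoms beforehand has little room to answer item 2 above its midpoint. A patient who was not limited beforehand is offered the top score on item 3. If this between-patient variation is predictable from pre-operative pain and urinary symptoms, leaving those out of the model makes the arm comparison at each visit less precise than it could be.

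A second gap touches the same sentence of the plan. A time-by-arm interaction asks whether the arm difference changes between 7 days and 4 weeks. If silicone improved satisfaction by the same amount at both visits, the interaction would be zero although both hypotheses in Section 5.4 were true. The stated aim of detecting a difference at either time therefore needs contrasts at each visit, and those are the contrasts that baseline adjustment can sharpen.

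**Working it through.** **1. The plan's own figure.** Section 11.2 gives 101 per arm for a 5-point difference, SD 10, two-sided alpha 0.025 and 90% power. The noncentral t distribution gives 90.1% at 101 per arm and 89.8% at 100, so 101 reproduces. Allowing for 10% loss, 202 / 0.90 = 224.4, in line with the planned 224. None of this concerns ICIQ-S, for which the plan states no SD, effect size, alpha or power.

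**2. Share of the score tied to the pre-operative state.** The printed maxima are 4 + 4 + 3 + 4 + 4 + 5 = 24. Items 2 and 3 carry 4 + 3 = 7, and 7 / 24 = 29%. The document prints no scoring rule, so the total of 24 is a plain sum of the printed options.

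**3. Arm difference at one visit.** Assumptions: 101 evaluable per arm, two-sided alpha 0.05, a true difference of 0.4 SD, and correlation r between the baseline covariate(s) and ICIQ-S (for two covariates, read r as the multiple correlation). Adjustment multiplies the residual variance by 1 − r². In SD units the standard error is √(2/101) × √(1 − r²), and the effective standardised difference is 0.4 / √(1 − r²).

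| r | 1 − r² | SE (SD units) | Power |
|---|---|---|---|
| 0 | 1.00 | 0.141 | 80.8% |
| 0.1 | 0.99 | 0.140 | 81.1% |
| 0.2 | 0.96 | 0.138 | 82.3% |
| 0.3 | 0.91 | 0.134 | 84.3% |
| 0.4 | 0.84 | 0.129 | 87.0% |
| 0.5 | 0.75 | 0.122 | 90.4% |

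**4. Time-by-arm interaction.** This is the arm difference in the within-patient change between visits. If baseline has the same effect at both visits, it cancels from the change. A simulation of 4,000 trials, with an assumed between-visit correlation of 0.5, gave these standard errors for the interaction:
- r = 0.3: 0.140 without the covariate, 0.141 with it.
- r = 0.5: 0.143 without, 0.143 with.

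In the same runs the standard error of the single-visit difference fell from 0.139 to 0.134 at r = 0.3 and from 0.144 to 0.124 at r = 0.5. The gain belongs to the differences at each visit only.

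**5. How large r might be.** Greater pre-operative burden leaves more room to score high on item 2, while absence of limitation favours the top score on item 3, so the two can offset. As an illustration, let item SDs be proportional to their maxima, inter-item correlation be 0.3 to 0.5, and only items 2 and 3 relate to baseline, each at 0.3 to 0.5 in absolute value. The sum of squared maxima is 98. The total's variance is 98 + 0.3 × (576 − 98) = 241.4 (SD 15.5) or 98 + 0.5 × 478 = 337 (SD 18.4). The correlation of the total with baseline is then:
- items opposed: 0.3 × (4 − 3) / 18.4 to 0.5 × (4 − 3) / 15.5 = 0.02 to 0.03;
- item 2 only: 0.3 × 4 / 18.4 to 0.5 × 4 / 15.5 = 0.07 to 0.13;
- items aligned: 0.3 × 7 / 18.4 to 0.5 × 7 / 15.5 = 0.11 to 0.23.

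The upper rows of the table would need baseline to relate to the other four items as well. That is possible, but the documents give no evidence either way.

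**The case against.** The case for leaving the plan alone is substantial. Satisfaction is exploratory, carries no power claim, and changes no primary or secondary conclusion. The plan is silent on covariates rather than ruling them out. The primary ANCOVA is an imperfect precedent: it adjusts each PROMIS score for its own baseline, whereas ICIQ-S asks about surgery already done and can have none. (The reference to a baseline ICIQ-S score in the postoperative assessments of Section 8.3 looks like a wording slip.) PROMIS pain and LURN SI-10 are proxies, and step 5 shows that their correlation with the total could be negligible. All of this stands, and it sets the size of the point.

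It does not remove the point. Section 5.4 asks about each visit, the interaction does not answer that, and the contrasts at each visit are where adjustment can help.

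Two stronger readings are tempting. A reader might infer that the unadjusted satisfaction comparison is biased by pre-operative state. The documents do not support that: allocation is randomised 1:1, and the unadjusted confidence interval already allows for chance imbalance. A reader might also infer that the ICIQ-S score as a whole is measured against the pre-operative state. Only two of six items are worded so; 17 of the 24 points are not. Even on item 3, a patient not limited beforehand but limited by the stent may still tick a lower category.

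**Conclusion.** The point holds as a minor, optional improvement to an exploratory analysis. The ICIQ-S model names no baseline covariate although relevant pre-operative scores are collected, and its named test does not deliver the comparisons that Section 5.4 states. The cost is possible loss of precision at each visit, with no bias. Relative to 80.8% power unadjusted, the gain ranges from nothing at r = 0 to 9.6 percentage points at r = 0.5, and is 0.3 points at r = 0.1. These figures rest on an assumed 0.4 SD difference, two-sided alpha 0.05, 101 evaluable patients per arm at the visit, and an r that the documents do not give. The interaction test gains nothing if baseline acts equally at both visits. Confidence that the gain is material is low.

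**What to change.** In the ICIQ-S paragraph of Section 11.4 (Exploratory Analyses), add the pre-operative PROMIS pain interference t-score and the pre-operative LURN SI-10 score as covariates. State that the baseline-adjusted arm difference, with its confidence interval, will be reported at 7 days and at 4 weeks alongside the interaction test. Naming the covariates before the data are seen also avoids a post-hoc choice.

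The cost is one sentence and two model degrees of freedom. No new data are needed, and few covariate values should be missing if the baseline questionnaire is completed before surgery as Section 7 expects. If r proves to be near 0, almost nothing is lost.
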